### 13.2. Futility Analysis

The interim futility analysis comprises a statistical comparison between treatment group versus placebo in LoAC rate using logistic regression among the randomized patients who have completed the treatment period, experienced LoAC, or withdrawn from the study completely at time of the interim analysis. The logistic regression model will include fixed effect for treatment, age group (<65 years vs  $\geq 65$  years) and gender, as well as baseline FEV1 and baseline weight as covariates. A one-sided p-value above 0.5 will be declared as treatment efficacy futility, which could potentially result in early termination of the trial. According to simulation analyses, this cutoff value yields a correct early termination rates under the null hypothesis of 0.43 (40 patients) and 0.44 (52 patients) and controls incorrect early termination rate under the alternative hypothesis at approximately and 0.06 (40 patients) and 0.04 (52 patients). The following table provides the correct early termination rates (under the alternative hypothesis) and the incorrect early termination rates (under the null hypothesis) at different interim analysis time points and using different p-value cut-offs, calibrated through simulations. The placebo LoAC rate is assumed to be 0.27.

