9.13. Planned Interim Analyses

An unblinded interim analysis is planned after the first 40 to 52 randomized patients have completed the treatment period, experienced LoAC, or withdrawn from the study completely. The main purposes of the interim analysis include sample size re-assessment and futility analysis, as described below.

The assumed LoAC event rate in the placebo group is 0.270. If the actual placebo event rate is lower than expected, the study will be underpowered to detect a 60% reduction in event rate. At the interim analysis, if the observed placebo event rate is lower than expected, and the observed treatment effect is at least a 40% reduction (event rate ratio ≤ 0.6), the sample size may

be increased by up to 50 additional randomized patients, from the initially planned 124 to up to 174. This procedure corresponds to a Promising Zone methodology and does not increase the Type I error rate (Mehta and Pocock, 2011).

The interim futility analysis comprises a statistical comparison between treatment group versus placebo in LoAC rate using logistic regression with fixed effect for treatment among the randomized patients who have completed the treatment period, experienced LoAC, or withdrawn from the study completely at the interim analysis. A p-value above 0.5 will be declared as treatment efficacy futility, which could potentially result in early termination of the trial. According to simulation analyses, this cutoff value yields correct early termination rates under the null hypothesis of 0.43 (40 patients) and 0.44 (52 patients) and controls incorrect early termination rate under the alternative hypothesis at approximately 0.06 (40 patients) and 0.04 (52 patients). More details will be provided in a separate Interim Statistical Analysis Plan that will be finalized prior to the interim analysis.

The interim analysis will be conducted by an independent, unblinded statistician who is not a part of the study team. A group of the sponsor's management team who are not a part of the study team may have access to the unblinded interim analysis results. A communication plan to ensure the maintenance of the study blind among the blinded personnel involved in the conduct of the study will be put in place prior to the interim analysis.

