**Table 6: Correct and Incorrect Early Termination Rates**

Interim Analysis Sample Size (Total)	P-Value Cut-Off	Correct Early Termination Rate	Incorrect Early Termination Rate
20	>0.5	0.40	0.12
20	>0.33*	0.60	0.25
30	>0.5	0.42	0.08
30	>0.33	0.58	0.18
40	>0.5	0.43	0.06
40	>0.33	0.57	0.13
52	>0.5	0.44	0.04
52	>0.33	0.56	0.09

\*0.33 cut-off shown for comparison purposes only; the actual futility cut-off is  $p > 0.5$

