#### **14. STATISTICAL SOFTWARE**

All data listings, summaries, and statistical analyses will be generated using SAS® version 9.4 or later.

**15. CHANGES TO ANALYSES SPECIFIED IN THE STUDY  
PROTOCOL**

None.

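### SAP 13.2 adjusts the futility test for four covariates but keeps the termination rates of an unadjusted, equal-arm comparison, and the sentence above Table 6 swaps the hypotheses

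*SAP*

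**What the plan says.** Protocol 9.13 compares LoAC rates at the interim "using logistic regression with fixed effect for treatment among the randomized patients who have completed the treatment period" or reached another qualifying status. It reports that "this cutoff value yields correct early termination rates under the null hypothesis of 0.43 (40 patients) and 0.44 (52 patients"), with incorrect termination of about 0.06 and 0.04 under the alternative.

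SAP 13.2 uses a different model: "The logistic regression model will include fixed effect for treatment, age group", gender, baseline FEV1 and baseline weight, the same covariates as the primary model in SAP 6.2.2. It makes the p-value explicitly one-sided and keeps the cut-off of 0.5. It then gives the same 0.43 and 0.44 under the null and says the rule "controls incorrect early termination rate under the alternative hypothesis at approximately and 0.06 (40 patients) and 0.04 (52 patients"). Table 6 carries the same four figures.

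The next sentence in SAP 13.2 says Table 6 shows "the correct early termination rates (under the alternative hypothesis) and the incorrect early termination rates (under the null hypothesis"), the reverse of the sentence before it. A p-value above the cut-off is a flag "which could potentially result in early termination of the trial", so the rule is non-binding. SAP section 15, headed "CHANGES TO ANALYSES SPECIFIED IN THE STUDY" protocol, contains only the word None.

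**The concern.** The SAP may change the futility model, and its Introduction says it takes precedence over the protocol. The error rates it reports should then belong to the model it specifies. Identical two-decimal rates under a treatment-only model and under one with four covariates suggest that the rates were carried over. These are the only operating characteristics the documents give for a rule that can end the trial. If they are wrong, those weighing a stop would read the flag against too low a chance of abandoning an effective drug. The reversed labels sit in the text that explains the table.

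**Working it through.** **Inputs.** Placebo LoAC rate 0.27 (SAP 13.2). Active rate 0.108 under the alternative (SAP 2.4) and 0.27 under the null. Allocation 1:1 (SAP 2.1). Interim at 40 to 52 patients in total, flag if one-sided p > 0.5 (SAP 13 and 13.2).

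**Reproducing the stated rates.** In a treatment-only logistic model, one-sided p > 0.5 means the observed active rate is strictly above the placebo rate. With x events out of n in each arm (A active, P placebo):

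P(flag) = Σ Bin(x_A; n_A, p_A) × Bin(x_P; n_P, p_P), summed over x_A/n_A > x_P/n_P.

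For equal arms (each cell null / alternative):

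| Total (per arm) | Active > placebo | Same, plus no events in either arm | Table 6, >0.5 | Active ≥ placebo | Table 6, >0.33 |
|---|---|---|---|---|---|
| 20 (10) | 0.400 / 0.103 | 0.402 / 0.117 | 0.40 / 0.12 | 0.600 / 0.254 | 0.60 / 0.25 |
| 30 (15) | 0.418 / 0.078 | 0.418 / 0.080 | 0.42 / 0.08 | 0.582 / 0.176 | 0.58 / 0.18 |
| 40 (20) | 0.429 / 0.059 | 0.429 / 0.059 | 0.43 / 0.06 | 0.571 / 0.127 | 0.57 / 0.13 |
| 52 (26) | 0.438 / 0.042 | 0.438 / 0.042 | 0.44 / 0.04 | 0.562 / 0.088 | 0.56 / 0.09 |

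All 16 entries of Table 6 match to two decimals if its >0.5 rows mean more events on active (or none in either arm) and its >0.33 rows mean at least as many. A treatment-only likelihood-ratio p > 0.33 would give, at 30, 40 and 52 patients, 0.699, 0.698 and 0.680 under the null and 0.221, 0.192 and 0.151 under the alternative. Table 6 therefore looks like a comparison of event counts in equal arms. That is an inference, because the documents do not describe the simulation.

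**Why the null rate is below one half.** With equal arms and tie probability t, symmetry gives P(flag) = (1 − t)/2. At 40 patients t = 0.571 − 0.429 = 0.142, so (1 − 0.142)/2 = 0.429. At 52, t = 0.562 − 0.438 = 0.124, so P(flag) = 0.438. Two continuous covariates remove nearly all ties, so t is close to 0 and the null rate is about 0.50 whatever the covariate effects.

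**The SAP's model under the alternative.** If the covariates merely broke ties at random, the rate would be (0.059 + 0.127)/2 = 0.093 at 40 and (0.042 + 0.088)/2 = 0.065 at 52. The adjusted model was also simulated, with 8,000 interims per case and marginal rates held at 0.27 and 0.108. Assumptions not in the documents: 5–25% aged 65 or over, 30–50% male, FEV1 log-odds ratio per SD of 0, 1.0 or 1.5, and one case with age and sex effects of 0.7 and 0.5.

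- Null: 0.488–0.510 in all cases.
- Alternative, equal arms: 0.079–0.106 (40) and 0.049–0.073 (52).
- Alternative, simple allocation: 0.083–0.104 and 0.054–0.070.

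Monte Carlo standard errors are about 0.006 (null) and 0.003 (alternative). Separated fits were handled by a small ridge penalty or by Firth's method, with results differing by at most 0.005. A second simulation (15% aged 65 or over, 60% one sex, FEV1 effect 0, 0.5 or 1 per SD) gave 0.093–0.116 and 0.063–0.079 under the alternative.

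**The protocol's model with unequal arms.** Exact alternative rates (active/placebo): 0.079 at 21/19, 0.098 at 19/21, 0.056 at 27/25, 0.069 at 25/27; null 0.495–0.505. Weighting over simple 1:1 allocation gives 0.486 / 0.086 at 40 and 0.489 / 0.062 at 52. Arms are then exactly equal in only 12.5% and 11.0% of interims.

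**Power lost if every flag were followed** (final chi-square test, one-sided 0.1, 52 evaluable per arm, total power 0.807), at 40 and 52 patients: rule as stated, 0.019 and 0.008; treatment-only with simple allocation, 0.033 and 0.016; adjusted model, 0.036–0.049 and 0.018–0.024.

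**The case against.** Several points can be made for the plan.

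- **Ties.** A p-value must be above 0.5 to count, so a tie already means continue. That is the literal reading and no error for a treatment-only model. The 20-patient row even needs an empty-arms tie counted as stop.
- **Equal arms.** These are a normal planning assumption under 1:1 allocation. The randomization specification is not in these documents, so blocking may exist. However, SAP 13.2 analyses patients by outcome status, so even a balanced list need not give equal arms. Taking the first 40 finishers from balanced cohorts of 48 to 124 patients gives 0.080–0.085 under the alternative, and the first 52 from cohorts of 60 to 124 gives 0.056–0.060.
- **Assumed covariates.** The alternative rates rest on assumptions and on ridge or Firth fits the SAP does not name. The lower ends, 0.079 and 0.049, are within two points of 0.06 and 0.04, which the text calls approximate. This stands as a limit on the size, but not on the null rate, which needs only exchangeable arms and few ties.
- **Power loss.** The calculation uses 52 per arm and a chi-square test, while the primary analysis is an adjusted model on all randomized patients. With 62 per arm, the equal-arm treatment-only rule loses 0.028 and 0.015 instead of 0.019 and 0.008. The power figures are therefore indicative only.
- **Other documents.** The Interim SAP or charter may hold correct rates, but that would not make the SAP's figures right.
- **The >0.33 rows.** Table 6 marks this "cut-off shown for comparison purposes only; the actual futility cut-off is" p > 0.5, so those rows affect no decision.
- **Labels.** A careful reader can recover the meaning from the preceding sentence.

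None of this explains how two different models share four identical rates.

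**Conclusion.** The point holds. The rates in SAP 13.2 and Table 6 do not describe the futility rule the SAP specifies. The chance of a correct futility flag is about 0.50 rather than 0.43 or 0.44, so it is understated by 6 to 7 points. The chance of a false flag is understated by about 1 to 5 points on the main covariate assumptions. The first figure is firm; the second depends on the assumed covariates.

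The covariates are not the whole story. Under simple allocation, adjustment moves the alternative rate by only −0.008 to +0.018 from the treatment-only value, so the equal-arm and tie conditions matter at least as much. Restoring the protocol's model would not by itself recover the stated rates.

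The label swap is a plain contradiction in wording; the table's values follow the earlier sentence. Because the flag is non-binding and the null discrepancy means more stops for an ineffective drug, the consequence is modest. It is still worth correcting before the interim.

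**What to change.** In SAP 13.2, re-simulate the futility rule with the model that will be used, stating the allocation, tie, zero-event, covariate and separation assumptions. A separation rule is needed: in the simulations under the alternative, some level of treatment, age group or sex had no events or only events in 23–68% of interims at 40 patients and 12–63% at 52.

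Replace the four rates in the text and in Table 6 with the results, and recompute or delete the >0.33 rows. List the change from protocol 9.13 in SAP section 15, and name the same model in the interim charter and Interim SAP.

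If the treatment-only model is preferred, restore it, give its rates for realistic interim arm sizes and say that p = 0.5 means continue. Either way, reword the sentence above Table 6 so that correct termination is tied to the null and incorrect termination to the alternative.

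The cost is one short simulation and a few wording changes before the interim, with no effect on data collection or conduct. The stated false-futility rate will look less favourable.

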**Table 6: Correct and Incorrect Early Termination Rates**

Interim Analysis Sample Size (Total)	P-Value Cut-Off	Correct Early Termination Rate	Incorrect Early Termination Rate
20	>0.5	0.40	0.12
20	>0.33*	0.60	0.25
30	>0.5	0.42	0.08
30	>0.33	0.58	0.18
40	>0.5	0.43	0.06
40	>0.33	0.57	0.13
52	>0.5	0.44	0.04
52	>0.33	0.56	0.09

\*0.33 cut-off shown for comparison purposes only; the actual futility cut-off is  $p > 0.5$

#### **14. STATISTICAL SOFTWARE**

All data listings, summaries, and statistical analyses will be generated using SAS® version 9.4 or later.

**15. CHANGES TO ANALYSES SPECIFIED IN THE STUDY  
PROTOCOL**

None.

